### 5.3 STRATEGIES FOR RECRUITMENT AND RETENTION

Recruiting will be performed mainly at Weill Cornell Medical Center which is closely affiliated with HSS and MSKCC providing additional access to patients. Dermatologists at Weill Cornell Medicine will be primary sources of referral within the department. In addition, [name] MD, MS, Transplant Nephrologist and Medical Director, Histocompatible Transplant Program will help recruit transplant patients from their transplant center.

Each patient regarding of study arm will receive \$50 for each visit for a maximum of 3 visits. Patients in the study arm who use the device on a consistent basis (>40% of days per month with no gaps longer than seven days) will receive \$20 per month for up to 12 months.

The sponsor may offer additional prize based motivations for use which will not exceed \$1,000 for any single subject in a given month.

## 5.4 PARTICIPANT WITHDRAWAL OR TERMINATION

Participants may withdraw for any reason during the study.

### 5.4.1 REASONS FOR WITHDRAWAL OR TERMINATION

Participants who can not comply with the requirement for quarterly visits will be dropped from the study.

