## 4 STUDY DESIGN AND ENDPOINTS

### 4.1 DESCRIPTION OF THE STUDY DESIGN

This randomized partially blinded study will recruit 120 patients with a history of actinic keratosis (AK) lesions. A control versus study group analysis will be performed where 50% of the subjects will be randomly assigned (balanced by Fitzpatrick skin type, separate randomization lists will be made for type I&II and types III-VI, at time of first visit subjects will be assigned to study or control group by giving them the next assignment on the appropriate list) to use the SHADE sensor and its app (study group), while the other 50% (control group) will receive standard of care UV counseling(placebo). Subjects will have 3 visits. The first and last visit will be standard of care visits at 0 month (enrollment), and the conclusion of their involvement. The second visit will be scheduled 3 months after the enrollment visit. The final visit will be scheduled as soon as practical, but at least 3 months after visit 2 and after September 30. On arrival at each visit, study personnel will pre-screen patients to ensure that the sensor is not visible to physician prior to examination, for example by placing it in their pocket. At each follow up visit, the number of actinic keratosis on the face and hands will be counted and photographed. They will be treated as per standard of care protocol with cryotherapy or curettage. General use of field therapies will not be permitted during the trial. Any lesions suspicious of non-melanoma or melanoma skin cancer will be photographed and biopsied as part of the standard of care algorithm. Cyclobutane pyrimidine dimers (CPD) levels will be measured by ELISA from exposed (cheek) and unexposed (buccal mucosa) skin scrapings collected at the first and last visit. For each patient, the CPD level from exposed skin will be normalized to the sun protected CPD level measured from unexposed skin. We will compare the normalized CPD level of control versus study participants at each timepoint and their average CPD change over time.

We will then compare these levels with Shade UV measurements. Finally, patients will also answer questions in PROMIS (Patient-Reported Outcomes Measurement Information System) in the fields of anxiety, depression and ability to participate socially to gauge their attitudes toward the sensor

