### 5.4.2 HANDLING OF PARTICIPANT WITHDRAWALS OR TERMINATION

Subject compensation will not be affected by study withdrawal or termination. Each endpoint will be analyzed using only data for which there is a complete data set relevant to that analysis.

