### 7.3.5 EARLY TERMINATION VISIT

Subjects who withdraw consent or otherwise voluntarily leave the study will be offered the opportunity to participate in the next visit scheduled for the study.

Subjects who are dropped from the study for any reason will be contacted by phone to explain the reason they have been dropped from the study. An early termination visit is not required.

Subjects who terminate early will be asked to return their Shade device and will be given the same offer to obtain a new device of their own as subjects who complete the study.

The study coordinator will fill out a study termination form for all subjects including those who leave early.

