### ***10.4 DESCRIPTION OF STATISTICAL METHODS***

Actinic keratosis (AK) is a frequent pre-cancerous skin lesion caused by damage from ultraviolet exposure. Without treatment, 1-2% of these lesions evolve into squamous cell carcinoma (SCC). Therefore, the number of AKs reflects the effect of UV exposure and the risk for SCC. Transplant patients are at high risk of skin cancer because of their immunosuppressive medications required to prevent organ rejection. Morbidity/mortality of SCC in this patient population can be as high as 25%.

The primary outcome of this trial will be a statistically significant reduction by at least 25% in the cumulative number of newly developed AK lesions between the control and the study group.

AK lesions on sun exposed skin areas (scalp, face, hands) will be counted and reported by dermatologists at enrollment and at each subsequent visit. AKs are defined as keratotic macule(s) or papule(s) on an erythematous base by dermatological examination. In addition to the enrollment visit, this study will include a follow up dermatological visit after the summer. For each patient, the number of newly occurred AKs will correspond to the cumulative AK counts during the study period. To insure that only new occurrences of AK lesions after V1 will be counted, data from subsequent study visits will include the location of AK lesions and pictures of the lesions.

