#### 10.4.5 ADHERENCE AND RETENTION ANALYSES

See specific Aim #8.

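### The quarterly-visit drop rule in 5.4.1 does not fit the three-visit design and, with 7.3.5 and 5.4.2, can lose randomised patients to the primary endpoint while they could still attend the final visit

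*Combined protocol and SAP*

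**What the plan says.** **Removal.** Section 5.4.1: "Participants who can not comply with the requirement for quarterly visits will be dropped from the study". The ongoing criteria in 5.2 also remove a subject who cannot keep to the continuing visits, but leave the decision to the PI when the change in status lasts less than three months.

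**Schedule.** Section 4.1 sets the number: "Subjects will have 3 visits". V1 is enrolment and V2 falls at month 3. For V3 the rule is: "The final visit will be scheduled as soon as practical, but at least 3 months after visit 2 and after September 30". Inclusion criterion 4 in 5.1 asks for three dermatology visits and names no interval. Section 14.3 allows a visit to move by up to 21 days from target without being reported as a deviation.

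**After removal or withdrawal.** Under 7.3.5, subjects who leave voluntarily "will be offered the opportunity to participate in the next visit scheduled for the study". Subjects dropped by the study get a telephone explanation, and no termination visit is required.

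**Analysis.** Section 5.4.2: "Each endpoint will be analyzed using only data for which there is a complete data set relevant to that analysis". The primary variable is the cumulative count of new AKs after V1 (10.4, 10.4.2). The final-visit count alone is secondary endpoint #2 (10.4.3).

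**Retention.** Section 10.4.5 reads "See specific Aim #8". Aim #8 is the PROMIS quality-of-life endpoint. Sensor usage is #9, and #10 reports retention for kidney transplant recipients only.

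**The concern.** The drop rule enforces a requirement that the current schedule does not contain. A site applying it literally could remove a patient who cannot make V2 although the post-summer visit could still be held. The patient has not withdrawn consent, yet no later AK count is sought. That costs the primary endpoint, and also secondary #2, for which the final visit alone would have been enough.

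The early-termination rule does not repair this. A patient who leaves before V2 is offered V2, which does not cover the rest of the summer. Section 5.4.2 may then set that count aside as incomplete.

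At stake are the number of patients analysed and the comparability of the arms. If reasons for missing visits differ by arm, the primary comparison becomes one of completers, and no planned table would show it.

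**Working it through.** **1. Does the schedule allow quarterly visits?** Inputs from 4.1: V2 = enrolment + 3 months; earliest V3 = the later of V2 + 3 months and October 1. September 30 is read as the end of the follow-up summer. The enrolment dates are illustrations.

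| Enrolment | V2 | Earliest V3 | V2-to-V3 gap |
|---|---|---|---|
| Nov 1 | Feb 1 | Oct 1 | 242 days |
| Jan 15 | Apr 15 | Oct 1 | 169 days |
| Mar 1 | Jun 1 | Oct 1 | 122 days |
| Apr 1 | Jul 1 | Oct 1 | 92 days |

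Before about April 1, 4.1 itself rules out a quarterly V3. The 21 days in 14.3 move the limit only to about March 10 (V2 June 10; plus 3 months, September 10; plus 21 days, October 1). From April onward the visits can be about quarterly. Over the 9–12 months of use in 6.1.9, a true quarterly schedule would need four or five visits, not three. Section 17.2 records that later visits were removed, so the word is probably a remnant.

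**2. What happens to the patient's data?**

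| Route | Offered under 7.3.5 | Primary count | Secondary #2 |
|---|---|---|---|
| Dropped under 5.4.1 | No visit | Lost | Lost |
| Leaves before V2 | V2 | Incomplete | Lost |
| Leaves after V2 | Final visit | Obtainable | Obtainable |
| Misses V2, kept in study | Final visit | Not defined | Obtainable |

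The last row is a gap: no section says how the cumulative count is formed without V2.

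**3. How close is V3 alone to the cumulative count?** Assume equal numbers of new AKs before and after V2, and that a share p of the first-interval lesions is still present at V3. V3 then captures (1 + p)/2 of the total:

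- p = 1: 100%
- p = 0.8: 90%
- p = 0.5: 75%

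The documents give no value for p. High persistence is plausible, because treatment by an outside dermatologist is prohibited (7.6). Earlier photographs are re-read to avoid double counting (7.1.1). If a share m of one arm lacks V2 and those patients are otherwise like the rest, that arm's mean is understated by m(1 − p)/2. With m = 10% and p = 0.5 (both assumed) this is 0.10 × 0.25 = 2.5%.

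**4. What margin is there?** Section 10.5 states power 0.81 with 100 patients and an effect of 0.25. This cannot be reproduced, because the AK distribution used in the simulation is not given. Recruitment is 120. If the 100 are read as patients analysed, the margin is 1 − 100/120 = 16.7%.

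For illustration only, the standardised difference that returns 0.81 one-sided at 50 per arm is (1.645 + 0.878) × √(2/50) = 0.505. With power = Φ(0.505 × √(n/2) − 1.645), and overall losses assumed from 0 to 25%:

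| Loss from 120 | n per arm | Power, one-sided |
|---|---|---|
| 0% | 60 | 0.87 |
| 10% | 54 | 0.84 |
| 16.7% | 50 | 0.81 |
| 25% | 45 | 0.77 |

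The analysis is two-tailed (10.4.1). That mismatch with the simulation is a separate matter.

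**The case against.** **The rule is softer than it looks.** Section 5.4.1 concerns participants who cannot comply, not everyone who misses one visit. The PI discretion in 5.2 and the 21-day allowance in 14.3 would keep many patients in. This stands, and it is why the loss cannot be sized. But 5.4.1 itself contains no discretion, and the discretion in 5.2 covers only temporary changes.

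**The date gaps do not show lost patients.** A reader might infer that sites will drop early enrollees whose V3 falls long after V2. The documents do not support that: such a V3 is what 4.1 requires. The dates show a conflict of wording only.

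**The primary count is not simply recoverable at V3.** A reader might infer that it is, since 10.4 says that "this study will include a follow up dermatological visit after the summer". The same section has AKs counted at each subsequent visit, and 10.4.3 makes the final-visit count a separate endpoint. V3 alone is an approximation. At p = 0.5 the individual shortfall is 25%, as large as the target reduction.

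**A headcount of avoidable loss is fragile.** With 10% missing each visit independently, requiring both leaves 120 × 0.9 × 0.9 = 97, against 120 × 0.9 = 108 for V3 alone. If everyone who misses V3 also missed V2, both rules leave 108. The 97 also assumes that every missed V2 leads to removal or exclusion. No conclusion here rests on this contrast.

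**Attrition need not differ by arm.** Visit payments are the same, $50 per visit (5.3), and the coordinator contacts all subjects about visits (7.3.3). The monthly payments reward wearing the sensor, not attendance. This stands, so bias is possible but not shown. Only the study arm has usage payments, compliance support and the burden of the sensor. A termination form is completed for every subject (7.3.5) and group is in the dataset (10.4.10), so retention by arm could be tabulated, but no such table is planned.

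**Conclusion.** The point holds as a conflict between sections with a real but unquantified consequence. Section 5.4.1 enforces a visit requirement that 4.1 and 5.1 do not set and that 4.1 makes impossible for enrolment before about April 1. Read with 7.3.5 and 5.4.2, it allows randomised patients who have not refused contact to leave without a final AK count. The removal and missing follow-up can arise at any enrolment date.

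The documents give no dropout rate and do not define a complete data set for the primary endpoint, so neither the number lost nor the direction of any bias can be stated. On the assumed calibration above, overall loss of up to 25% lowers one-sided power from 0.87 to 0.77. How much of any loss would come from the drop rule is unknown. The change should be made because it is cheap and protects the randomised comparison.

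**What to change.** - **5.4.1 and 5.2:** reconcile both visit-related removal rules with the three-visit schedule in 4.1, so that a missed or late V2 is not a reason for removal.
- **7.3.5:** invite every randomised patient who has not refused contact to the post-September-30 visit for the AK count, including those who miss V2 or leave early.
- **5.4.2:** state that a patient with V3 but no V2 enters the primary analysis with the new AKs since V1, identified from the V1 photographs, as an approximation of the cumulative count. Add two sensitivity analyses: one restricted to patients with both visits, and one that adds V2-only patients with their follow-up time.
- **10.4.5:** correct the cross-reference, and report retention and reasons for loss by arm.

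The cost is protocol wording and, for each patient retained, one visit already in the schedule. The downside is that, in patients without V2, lesions that arise and clear before V3 are missed, by an amount the documents do not allow one to estimate. The analysis restricted to patients with both visits is there to check whether this matters.

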### 5.4.2 HANDLING OF PARTICIPANT WITHDRAWALS OR TERMINATION

Subject compensation will not be affected by study withdrawal or termination. Each endpoint will be analyzed using only data for which there is a complete data set relevant to that analysis.

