#### 10.4.1 GENERAL APPROACH

All tests will be two-tailed with the significance level set at 0.05. Analysis will be performed using STATA statistical software (StataCorp. 2015) or R (R: A language and environment for statistical computing. R Foundation for Statistical Computing, Vienna, Austria).

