#### 10.4.2 ANALYSIS OF THE PRIMARY EFFICACY ENDPOINT(S)

##### **#1 (Primary): Quantify the impact of Shade on the cumulative number of new actinic keratoses developed over the study period.**

To test our primary aim, we will perform a control versus study group analysis. The study group will receive a Shade sensor and Shade app while the control group will standard of care sun avoidance counseling. The study will be randomized and single-blinded as described in section 10.6.1. This will also allow us to control for the effect of UV level variation on the primary outcome since the two groups will have balanced enrollment dates. All the patients will receive recommendations about UV exposure protection as defined by the recommendations of the American Academy of Dermatology and the National Cancer Institute.

Patients who will have used the Shade sensor for less than 15% of the days over the study period will be excluded from these analyses. We will use a Student's t-test with the following null and alternative hypothesis:

$$H_0: \text{mean}^C_{t12} (\text{AK}) = \text{mean}^I_{t12} (\text{AK})$$

$$H_a: \text{mean}^C_{t12} (\text{AK}) \neq \text{mean}^I_{t12} (\text{AK})$$

where  $\text{mean}^C_{t12} (\text{AK})$  is the averaged cumulative number of AK between enrollment follow up of controls and  $\text{mean}^I_{t12} (\text{AK})$  is the averaged cumulative number of AK of intervention patients.

In this analysis, demographic and clinical factors such as gender, age, baseline count of AKs, skin type, immunosuppressive treatment and comorbidity can be confounding factors. To test and control for confounding, demographic and clinical data (skin type, living area, gender, age, count of AK at enrollment, immunosuppressive (IS) treatment, level of immunosuppression and comorbidity) will be collected. We will use a stepwise multivariate approach with backward selection: 1) the effect of potential confounding factors will be tested using the same statistical tests, 2) factors with p-value <0.2 and less than 25% of missing values will be included in the multivariate model and 3) only covariates with significant adjusted p-value (<0.05) will be kept in the final model. Clinically relevant interactions will also be tested (e.g. skin type, gender, age) and kept in the final model if significant. The adjusted effect of Shade use will be estimated using a multivariate linear regression.

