### 10.5 SAMPLE SIZE

The most efficient approach to performing the power calculation for this study via Monte Carlo simulation as the underlying phenomenon, AK rate, is best modeled by a Poisson distribution.

As a starting point, we took the distribution of AK rates from actual clinical data. The data were assembled by querying EPIC on 2014 visits of kidney transplant patients to dermatology (this subset of the population will have fewer AK's than the non-transplant subjects and therefore use of this distribution will err on the side of caution toward overpowered the study). For each visit in which the dermatologist chose to treat by LN2 destruction, the query retrieved the number of procedures performed. This approach is conservative as the input data potentially underestimates AK count as some AK's may not have been treated.

The structure of the Monte Carlo was straightforward. A set of potential study sizes (N recruited) and effect sizes were chosen. For each input condition, two thousand random experiments were performed. In each of these interactions, baseline AK rates were drawn from the clinically observed distribution of AK's. Subjects were sequentially assigned to treatment or control groups. Observed AK rates were generated using a Poisson distribution for each visit. The analysis expected for the study was then performed. In this analysis the total count of AK's for each subject was obtained and the means and distributions compared for directionality (AK\_treated < AK\_control) and significance (p-value from a one-tailed t-test).

Analysis was performed in R (R Open 3.2.3) with statistical calculations and random number generation using the base and stat libraries.

[figure not shown]

Figure 10.5.1. With an effect size of 0.25 and recruitment of 100 patients (50 treatment, 50 control) we predict a power of 0.81.

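### On its natural reading, the complete-data rule makes the primary AK comparison a completers-only analysis with no missing-data sensitivity analysis, and it is biased if the pattern of leaving differs by arm

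*Combined protocol and SAP*

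**What the plan says.** Section 5.4 allows free withdrawal: "Participants may withdraw for any reason during the study". Section 5.4.2 then gives the only missing-data rule: "Each endpoint will be analyzed using only data for which there is a complete data set relevant to that analysis". It does not say what makes a set of AK counts complete.

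Section 4.1 schedules visit 2 three months after enrollment, and visit 3 at least three months after visit 2 and after September 30. AKs are recorded at both: "At each follow up visit, the number of actinic keratosis on the face and hands will be counted and photographed". Section 10.4 defines the outcome per patient: "the number of newly occurred AKs will correspond to the cumulative AK counts during the study period". Section 10.4.2 compares the arm means of these totals without adjusting for length of follow-up: "We will use a Student's t-test with the following null and alternative hypothesis". The analysis table in 10.4.10 has a single cumulative follow-up field for AK, whereas each PROMIS score has a field per visit.

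Section 7.3.5 offers voluntary leavers the next scheduled visit and requires no termination visit for patients who are dropped. The only longitudinal model in the plan is for squamous cell carcinoma (endpoint 3).

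**The concern.** A patient who leaves after visit 2 has a recorded count for part of follow-up but no full total. If that patient is dropped, the t-test estimates the effect among those who stayed to visit 3. The stated objective is the effect on new AKs over the study period.

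The two differ when the pattern of leaving differs by arm, and the design makes that plausible. Only the study arm wears and charges a device, receives alerts, is paid for regular use (5.3) and gets compliance calls (7.3.3). These could push retention either way. Patients know their arm and have their lesions marked and treated at each visit, so the visit 2 count could influence who returns.

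A shift of a few percentage points matters when the target is a 25% reduction. Setting aside observed counts also costs some precision, even if loss is random.

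**Working it through.** **Inputs from the documents.** 120 recruited, 1:1 (4.1). Power 0.81 for 100 patients and a 25% reduction (10.5), from a simulation using a one-tailed t-test. Planned tests: "All tests will be two-tailed with the significance level set at 0.05". Visit timing from 4.1; duration of use 9-12 months (6.1.9).

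**Assumptions.** No dropout rate or AK distribution is given. I assume loss of (120 − 100)/120 = 16.7%, all after visit 2, and gamma-Poisson counts. For bias, the control mean total is 4 to 8 and the gamma variance 0.1 to 0.25.

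**1. The plan's power figure.** "With an effect size of 0.25 and recruitment of 100 patients (50 treatment, 50 control) we predict a power of 0.81". This cannot be reproduced directly without the AK distribution, so I solve back from it, assuming one-sided 0.05:

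δ/SD = (z₀.₉₅ + z₀.₈₁) × √(2/50) = (1.645 + 0.878) × 0.2 = 0.5045.

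Power = Φ(0.5045 × √(n/2) − z), with n per arm:

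| Total N | One-sided | Two-sided |
|---|---|---|
| 120 | 0.868 | 0.789 |
| 100 | 0.810 | 0.713 |

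Gamma-Poisson simulations calibrated this way return 0.805-0.817 at 50 per arm, so 0.81 is plausible as a one-sided figure. Going from 120 to 100 patients costs 5.8 points one-sided and 7.6 two-sided. That is the cost of dropout as a whole.

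**2. The rule's share of the power loss.** Two-sided, 60 per arm, random one-sixth loss, equal intervals:

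| Control mean, variance | Completer t-test | Count model, completers | Count model, visit 2 kept |
|---|---|---|---|
| 4, 0.1 | 0.632 | 0.649 | 0.694 |
| 8, 0.25 | 0.605 | 0.628 | 0.676 |

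Keeping visit 2 data adds 4.5 and 4.8 points. The other 1.7 and 2.3 points come from changing the test. If follow-up is 9-12 months, visit 2 covers only 3/9 to 3/12 of it, and the gain falls to about 2 to 4 points.

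**3. Bias by hand.** If a fraction p leaves with log-odds β per SD of the visit 2 count, the completers' mean visit 2 count moves by about −β·p·SD. The visit 3 mean moves by that amount times the slope of visit 3 on visit 2. Take control mean 8, study mean 6, variance 0.25, equal intervals.

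- Study arm: variance per interval 3 + 0.25 × 3² = 5.25, SD 2.291, slope 2.25/5.25 = 0.429.
- Control arm: variance 4 + 0.25 × 4² = 8, SD 2.828, slope 4/8 = 0.5.
- Odds ratio 2, study arm only: shift 0.693 × (1/6) × 2.291 × 1.429 = 0.378. Estimate 1 − 5.622/8 = 29.7%.
- Odds ratio 0.67, study arm only (low-count patients leave): shift +0.221. Estimate 1 − 6.221/8 = 22.2%.
- Odds ratio 2 and one-sixth loss in both arms: control shift 0.693 × (1/6) × 2.828 × 1.5 = 0.490. Estimate 1 − 5.622/7.510 = 25.1%.
- Odds ratio 2 in both arms, 22% study versus 11% control loss: shifts 0.499 and 0.323. Estimate 1 − 5.501/7.677 = 28.3%.

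**4. Bias by simulation (true reduction 25%).**

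| Who leaves | Completer estimate |
|---|---|
| Random, equal loss | 25% |
| Same mechanism, equal loss | 24.7-25.6% |
| Study arm only, odds ratio 1.5-2 | 27.2-31.0% |
| Study arm only, odds ratio 0.67 | 22.3-23.4% |
| Odds ratio 2 in both arms, 22% vs 11% loss | 27.3-28.6% |
| Control arm only, log-odds 0.5 | 21.0-22.0% |

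The control-only row comes from the runs calibrated to power 0.81 (means 4 to 20). With no true effect and study-arm odds ratio 2, the completer test rejects in 0.08-0.10 of trials.

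**5. Using the visit 2 counts.** Predicting visit 3 from visit 2 within arm returned 24.8-25.4% throughout. An interval count model with a time offset reduces the bias but does not remove it: up to 26.4% at variance 0.25 and 27.7% at variance 0.5 when leaving depends on the visit 2 count.

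**The case against.** A reader might infer that the plan expressly deletes the visit 2 count. It does not: complete is undefined, and the cumulative field in 10.4.10 is not said to be empty for a patient seen only at visit 2. Deletion is the natural reading of 5.4.2 combined with a t-test on raw totals. A sponsor who intends to use partial counts would still have to say how.

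A reader might also infer that the rule takes the trial below its stated power, or costs 6 to 7 points. The documents do not support this. A 17% loss from 120 leaves 100, the number behind the one-sided 0.81, although the plan does not say that the extra 20 are for dropout. Most of the drop from 0.87 to 0.81 would be recovered by using visit 2 counts, but not all of it. A 6-to-7-point figure for the rule generally also credits it with a change of test. The lower two-sided figures reflect the one-tailed power simulation, which is a separate matter.

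The bias is also conditional. No dropout pattern is documented, visit 3 is a standard-of-care visit, and both arms are paid equally per visit. Unequal loss that is unrelated to the counts would not bias the completer means. Loss before visit 2 leaves no follow-up count to use, so assuming that all loss comes later favours the concern. These points limit the size of the problem. They do not supply a missing-data method, and extra recruitment does not remove bias.

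**Conclusion.** The point stands as a conditional one, and the plan should be changed. On the natural reading, the primary result rests on completers, recorded visit 2 counts are not used, and nothing tests how far this matters.

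Under the stated assumptions, a true 25% reduction moves to about 22% to 31% if leaving depends on the visit 2 count in one arm only, or if count-dependent loss is heavier in one arm. It is slightly lower, 21% to 22%, when the dependence sits in the control arm. Bias is negligible if loss and mechanism match. The power cost is secondary: about 5 two-sided points with equal intervals and about 2 to 4 if visit 3 is late. The 17% loss, its timing and the AK distribution are all assumptions. The documents do not show that such bias will occur, only that the plan neither prevents nor examines it.

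**What to change.** In 5.4.2 and 10.4.2, define a complete AK record and replace the complete-data rule for the primary endpoint:

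- **Primary analysis:** all randomised patients with at least one follow-up AK count. Multiply impute the missing visit count within arm from the baseline count and the observed follow-up count.
- **Missed visit 2 only:** the visit 3 count spans both intervals. Split it if the photographs allow lesions to be assigned to an interval; otherwise take it as the cumulative total.
- **Supporting analysis:** a count model with one record per interval, log-time offset and patient-level robust variance. Note that it is not fully protected when leaving depends on the visit 2 count.
- **Sensitivity analyses:** the completer t-test, and a not-at-random analysis that varies the imputed counts by arm.
- **Sample size:** state the dropout that recruiting 120 is meant to allow for.

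The exclusion of low sensor users in 10.4.2 is a separate question, but the new wording must be consistent with it. The cost is SAP text and a short program, with no new data, visits or patients. The small downside is that imputation assumes a missing count is predictable from the observed counts and arm, which is why the not-at-random analysis is needed.
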